10.2.2 Blood sampling procedures and parameters

It is recommended, for the sake of patient's comfort, to use butterfly needles and to place a catheter during the time of hospitalization for easy blood collection. Also, applying a topical anesthetic before catheter placement may be considered.

For central laboratory testing, the amount of blood taken per patient has been carefully considered, to reduce the burden as much as possible. For diagnostic testing, PK/PD analyses, and immunology testing, depending on the need, either 1.8, 2.7 or 4.5 mL of venous blood will be collected at the designated time points (see below and Appendix A), i.e. by using the smallest citrate-tube available. The routine laboratory safety parameters will be assessed in the local laboratories, and the required blood volume may vary between laboratories. At the set-up of the study, special attention will be given to minimize the required blood volume for this routine safety testing. The estimated volumes below are considered the maximally required sample volumes based on 5 mL collection tubes.

The typical amount of blood taken from a patient including a screening visit and following one HAE attack during the 90-day follow-up period will be a maximal volume of 30 mL according to the schedule below (see also appendix A). If subsequent attacks will be treated with the study medication, where PK/PD sampling is no longer scheduled, the volume of blood collection during the treatment period is estimated to account for a maximal volume of 25 mL for each additional attack.

If a 2 year old child was followed up for a single HAE attack (assuming an otherwise healthy child with a weight of 12 kg, and a whole blood volume of 80 mL/kg BW) the total volume of removed blood over a 3 month period would account for $30/960=3.1\%$ of total blood volume. For a 13 year old (assuming an average weight 44 kg and a whole blood volume of 75 ml/kg BW) this would be

Safety of Ruconest in 2-13 year old HAE patients

under 1%. It is generally accepted that blood loss should not exceed 3% of total blood volume over four weeks, and it should not exceed 1% of total blood volume at any single time⁽⁹⁾. In case of doubt, the investigator should ascertain that the hematocrit is not less than 38 volume%⁽¹⁰⁾.

| Blood sampling volumes | Screening | First Attack | Subsequent attacks |
|------------------------------------------------------------------------------------------|---------------|----------------------|----------------------|
| Screening diagnostics and immunology | 4.5 mL | | |
| Day of attack (immunology and PK/PD (only at first attack)) | - | 6.3 mL | 1.8 mL |
| Follow up visit at Day 28 (immunology) | - | 1.8 mL | 1.8 mL |
| Follow up visit at Day 90 (immunology) | - | 1.8 mL | 1.8 mL |
| Laboratory safety parameters (hematology/biochemistry) at baseline and Day 28 (4 x 5 mL) | - | 20 mL ⁽¹⁾ | 20 mL ⁽¹⁾ |
| Total | 4.5 mL | 29.9 mL | 25.4 mL |

(1) *Expected maximal volumes: hematology and biochemistry parameters are assessed by the local laboratories: the actual volumes may depend on the local laboratories' requirements and possibilities to minimize sample volume.*

Investigator review and sign off

Reports of all safety laboratory results (hematology, biochemistry, immunogenicity) will be reviewed, signed and dated by the investigator. The screening lab results must be reviewed and signed by the investigator to confirm eligibility prior to the administration of study medication.

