The reconstituted solution should be administered as a slow i.v. injection over approximately 5 minutes. A second dose can be provided, at the investigator's discretion, in case of insufficient therapeutic response. However, not more than two doses should be administered within 24 hours.

Main study parameters:

Safety and tolerability by standard criteria (vital signs, ECG, adverse events, routine laboratory safety parameters and immunogenicity (anti-host related impurities (HRI) and anti C1INH antibodies)

Efficacy parameters and endpoints (time to beginning of relief, time to minimal symptoms, time to complete resolution)

Pharmacokinetic and pharmacodynamic parameters (C1INH activity and C4 in plasma) during treatment for the first attack.

Nature and extent of the burden and risks associated with participation, benefit and group relatedness:

All study-related procedures must be hosted in a familiar environment in facilities selected for childcare: the staff must be trained in communicating to and looking after (young) children and their legal representatives. All study-related procedures (e.g. blood samplings) will be optimized and modeled in order to minimize risk and distress. Age appropriate information will be given to the child and his/her representatives prior to any investigations or procedures. Eventual changes in the procedures will be announced to them well in advance.

The level of risk may evolve over time, during the study and with evolving knowledge; as a consequence, Pharming Technologies B.V. (the Sponsor) will continuously monitor this aspect. By regularly reviewing accumulated outcome data from the pediatric clinical trial program the continuing safety of current participants and those yet to be enrolled will be ensured, as well as the continuing validity and scientific merit of the study.

To date, the only significant clinical risk associated with Ruconest is the possibility of allergic reaction. To reduce the risk of a drug-induced allergic reaction, all study patients are tested for IgE against rabbit epithelium (dander). Only patients who have been shown to have negative results for such test should be treated with Ruconest.

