7 STUDY POPULATION

7.1 Population (base)

Male and female patients, from 2 up to and including 13 years of age with a clinically suspected and/or confirmed diagnosis of HAE will be recruited for this study. Patients will be identified and invited to participate by the investigators at the respective study centers, if possible in close collaboration with the existing HAE Associations and/or other patient organizations and/or other referring physicians.

The criteria for the diagnosis of HAE will consist of a medical history supported by central laboratory investigations. The medical history of patients may include:

- self-limiting, non-inflammatory subcutaneous angioedema, without urticaria, often recurrent and often lasting more than 12h and/or
- recurrent self-remitting abdominal pain without clear organic etiology, often recurrent and often lasting more than 6h and/or
- recurrent laryngeal edema
- family members with recurrent angioedema and/or abdominal pain and/or laryngeal edema

A central laboratory will confirm the diagnosis of HAE, defined as:

- <50% of normal levels of C1INH activity

Secondary laboratory data supporting the diagnosis of HAE are:

- not abnormally low levels of C1q
- absence of C1INH auto antibodies (anti-C1INH IgM and IgG)

The results of secondary laboratory parameters in plasma collected at screening serves to exclude from the study patients with evidence for acquired angioedema (AAE) (by a level of C1INH activity <50% of normal, together with a low level of C1q and/or presence of anti-C1INH antibodies).

Patients will be qualified for recruitment in advance and will be instructed to report to the clinical centre as quickly as is safely possible at the onset of symptoms of an acute attack. The diagnosis of an HAE attack will be made by the investigator based on patient's and physician's experience and judgment, and the results of physical examination.

The results of non-invasive diagnostic procedures deemed necessary to exclude other pathologies (e.g. cholecystitis, pancreatitis, nephrolithiasis, appendicitis, peritonitis, salpingitis, trauma, allergies) and/or the results of study specific safety laboratory investigations should be recorded in the CRF. The results of the tests will thus serve to further ensure that a correct diagnosis of an HAE attack has been made.

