7.2 Inclusion criteria

Screening

- From 2 up to and including 13 years of age
- Clinical and laboratory confirmed diagnosis of HAE (baseline C1INH activity <50% of normal)
- Signed written informed consent (parental permission) signed by the legal guardian(s)

Treatment

- Clinical symptoms of an acute HAE attack
- Onset of eligible symptoms within 5 hours from the moment at which medical evaluation to determine eligibility has occurred
- IS score for at least one anatomical location at the time of initial evaluation of at least 3 (moderate severity or greater) without signs of spontaneous regression
- 24h or more have passed since the patient's last study treatment

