12.2 Variables

The following data will be considered in the analysis:

Safety

- immunogenicity data
- adverse events
- laboratory data (hematology, biochemistry).
- vital signs
- ECG

Efficacy

- time to beginning of relief on the basis of the overall severity VAS using the first time-point with a decrease of at least 20 mm at any eligible location, with persistence at the next time-point
- time to minimal symptoms assessed by using the overall severity VAS, defined as the first time point at which the overall severity VAS fall below 20 mm for all assessed locations
- time to beginning of relief on the basis of the IS using the first time-point with a decrease of at least one point at any eligible location
- time to minimal symptoms on the basis of the first time-point at which the IS reaches a value of one or less at all locations
- Time to beginning of relief on the basis of Question 1 and 2 of the TEQ, defined as the first time-point at which Question 1 is answered as a little better, better or much better and

Question 2 is answered as yes for the most severe eligible location, with persistence of these responses at the next time point

- Time to minimal symptoms on the basis of Question 3 of the TEQ, defined as the first time-point at which Question 3 is answered as yes for all locations
- time to complete resolution based on the time-point at which all symptoms at all locations have resolved
- therapeutic failure

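### The 30 mL blood maximum in Protocol 10.2.2 omits the 4.5 mL screening draw (34.4 mL in all), and the cited 1% single-time limit is never applied to planned maximum draws that exceed it in a 12 kg child

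*Protocol*

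**What the plan says.** Protocol Section 10.2.2 gives the burden of screening, one treated attack and follow-up to Day 90: "including a screening visit and following one HAE attack during the 90-day follow-up period will be a maximal volume of 30 mL". It converts 30 mL to 3.1% of blood volume for a 2-year-old of 12 kg at 80 mL/kg, and to under 1% for a 13-year-old of 44 kg at 75 mL/kg, over three months.

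It then cites two limits for blood loss. One is 3% of total blood volume over four weeks. The other is that "it should not exceed 1% of total blood volume at any single time". In case of doubt, the investigator is to verify a hematocrit of at least 38 volume%.

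The volume table in the same section has separate columns for screening (4.5 mL), first attack (29.9 mL) and subsequent attacks (25.4 mL). Of the 29.9 mL, 20 mL is the local hematology and biochemistry sample, 10 mL at baseline and 10 mL at Day 28. The volumes are described as "considered the maximally required sample volumes based on 5 mL collection tubes". The table footnote adds that actual local volumes may depend on the laboratories' "requirements and possibilities to minimize sample volume". The Synopsis promises that procedures such as blood sampling will be "optimized and modeled in order to minimize risk and distress".

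Section 7.2 admits patients "From 2 up to and including 13 years of age" and sets no minimum weight.

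**The concern.** There are two problems in one section.

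- **The total.** The sentence says that screening is counted, but the number it gives matches the first-attack column without screening. In a study of children from age 2, this figure tells an ethics committee or a parent how much blood will be taken.
- **The single-time limit.** The section quotes a 1% limit and prints every planned volume, but the only percentages it works out are three-month totals. A site that draws exactly the listed maxima from one of the smallest eligible children follows the schedule and still passes the limit quoted beside it. No sentence turns the general wish to minimize volumes into a volume limit for small children.

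**Working it through.** **Inputs**

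From the table in Protocol 10.2.2:
- screening 4.5 mL
- first-attack day, immunology and PK/PD, 6.3 mL
- Day 28 immunology 1.8 mL
- Day 90 immunology 1.8 mL
- local safety samples 20 mL (10 mL at each of two visits)

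From Appendix A, total per time point: screening 4.5, presentation 12.7, 5 minutes 1.8, 2-4 hours 1.8, Day 28 11.8, Day 90 1.8 mL.

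Blood volume from the section's own examples: 12 × 80 = 960 mL and 44 × 75 = 3300 mL.

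Appendix A's 12.7 mL at presentation equals 2.7 + 10. I therefore read the 2.7 mL tube as shared by immunology and PK/PD, which also fits 6.3 = 2.7 + 1.8 + 1.8.

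**1. Reproducing the stated figures**

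- First Attack column: 6.3 + 1.8 + 1.8 + 20 = 29.9 mL, which rounds to 30.
- 30/960 = 3.1% and 30/3300 = 0.9%, as stated.

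The stated figures are reproduced only when screening is left out.

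**2. Adding screening**

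- Table: 29.9 + 4.5 = 34.4 mL.
- Appendix A: 4.5 + 12.7 + 1.8 + 1.8 + 11.8 + 1.8 = 34.4 mL.
- Shortfall of the stated maximum: 34.4 − 30 = 4.4 mL; 4.4/34.4 = 12.8%.
- Shares with screening: 34.4/960 = 3.6%; 34.4/3300 = 1.04%.

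**3. Single draws against 1%, counted per time point**

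For the 12 kg child, 1% is 9.6 mL. At 80 mL/kg, the weight at which a draw equals 1% is volume/0.8.

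| Draw | Volume | Share at 12 kg | Above 1% below |
|---|---|---|---|
| First-attack presentation | 2.7 + 10 = 12.7 mL | 1.32% | 15.9 kg |
| Day 28, or presentation at a subsequent attack | 1.8 + 10 = 11.8 mL | 1.23% | 14.8 kg |

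**4. Dependence on the local sample**

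The actual local volume is not given. Assuming 4, 6, 8 or 10 mL, the first-attack presentation draw at 12 kg is 6.7, 8.7, 10.7 or 12.7 mL, that is 0.70%, 0.91%, 1.11% or 1.32%. Break-even local volumes at 12 kg are 9.6 − 2.7 = 6.9 mL at first-attack presentation and 9.6 − 1.8 = 7.8 mL at Day 28 or a subsequent attack.

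**5. If a single time means the whole treatment day**

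First-attack Day 0 is 12.7 + 1.8 + 1.8 = 16.3 mL. That is 1.70% at 12 kg and above 1% below 16.3/0.8 = 20.4 kg. Break-even for the local sample at 12 kg is 9.6 − 6.3 = 3.3 mL.

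**6. The four-week limit of 3% at 12 kg**

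- First-attack day plus Day 28, or plus a second attack day: 16.3 + 11.8 = 28.1 mL, 2.9%. This is met, with little room.
- A third attack day inside four weeks: 28.1 + 11.8 = 39.9 mL, 4.2%.
- Screening inside the same four weeks as the 28.1 mL: 32.6 mL, 3.4%.

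**The case against.** **The total is a wording slip.** The 4.5 mL and 29.9 mL stand in adjacent columns of the section's own table, and Appendix A lists every draw. Section 7.1 says "Patients will be qualified for recruitment in advance", so screening may fall well before the attack, and the 3.1% and under-1% figures fit the single-attack window they describe. This stands. No draw, endpoint or analysis changes; the sentence that says screening is included is what is wrong.

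**The single-time limit is partly handled.** The 1% limit is printed and scales with weight. The local volumes are planning maxima, site set-up is to give particular attention to reducing them, and a hematocrit check is available. This also stands in part: whether any draw passes 1% depends on what local laboratories take. But neither the set-up instruction nor the footnote sets a volume. The hematocrit check applies only in case of doubt and limits no volume.

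**Few children may be affected.** Section 4.1 gives a mean age at onset of 11.2 years, and treatment requires an Investigator Score of at least 3. The documents give no weight distribution, so the number of treated children below about 16 kg could be none or a few among the 20 or more planned. That limits the reach of the point, but the 12 kg child is the Protocol's own example.

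**Conclusion.** Both parts hold. The stated maximum is 4.4 mL, about 13%, too low for the period it names. The cited 1% limit is not applied, and the planned maximum draws exceed it at 12 kg by 0.32 and 0.23 percentage points when counted per time point.

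The second part rests on three assumptions: the Protocol's 80 mL/kg, the full 10 mL local sample, and a reading of single time that the Protocol does not define. Under the per-day reading the first-attack excess is larger (1.70%) and reaches children up to about 20.4 kg. At 75 mL/kg the weight thresholds rise to 16.9 kg (presentation), 15.7 kg (Day 28 or subsequent attack) and 21.7 kg (whole day).

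Three stronger inferences are not supported:

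- **That 3.1% is a miscalculation or breaches the 3% limit.** It is correct for attack to Day 90, and it covers three months while the limit covers four weeks. One attack plus Day 28 stays at 2.9%.
- **That small children will be overdrawn.** The listed volumes are upper bounds. Counted per time point, a local sample of 6 mL or less complies at 12 kg.
- **That the section has no safeguards.** It has set-up attention to local volumes and a hematocrit check. What it lacks is a volume limit.

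**What to change.** 1. Either state 34.4 mL including screening (3.6% at 12 kg, 1.04% at 44 kg), or delete the reference to the screening visit and label 29.9 mL, 3.1% and 0.9% as attack to Day 90.
2. Add a sentence requiring small-volume pediatric tubes for the local safety sample in small children, so that no single draw exceeds 1% of blood volume, and say how a single time is counted. At 80 mL/kg the local volume is then:
   - **per time point:** at most 0.8 × kg − 2.7 mL at first-attack presentation and 0.8 × kg − 1.8 mL at Day 28 or a subsequent attack (6.9 and 7.8 mL at 12 kg);
   - **per day:** at most 0.8 × kg − 6.3 mL on first-attack Day 0 (3.3 mL at 12 kg).
3. Ask sites to check the cumulative four-week volume against 3% before sampling a small child at a repeat attack.

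As an example, two 3 mL tubes in place of two 5 mL tubes give 8.7 mL (0.91%) at first-attack presentation and 7.8 mL (0.81%) at Day 28 for a 12 kg child. That satisfies the per-time-point rule. It does not satisfy the per-day rule, because Day 0 would be 6.3 + 6 = 12.3 mL (1.28%).

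The cost is a text correction, two added instructions and some tube supply. Hematology and biochemistry are safety variables in Protocol Section 12.2, so the panel should stay complete. Local laboratories must confirm at set-up that they can run all of it on the smaller volume. The documents do not say which can, and no safety data are lost only if they can.

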10.2.3 Assessment of efficacy

The assessment of efficacy will be based on the patient's and the investigator's assessment of angioedema signs and symptoms before administration of rhC1INH and the follow-up of changes in angioedema signs and symptoms at the symptomatic anatomical locations.

The severity of angioedema signs before and after the administration of rhC1INH will be rated by the patient or parent/legal guardian using VAS-scales. VAS completion by the patients is preferred. If needed, depending on the patient's level of understanding, parents may assist in completion. On the VAS-scales, it will be indicated if the score is completed by the patient or parent/legal guardian. Separate VAS forms will be given to express the current feelings considering the severity of angioedema symptoms for five possible anatomical locations: abdominal, urogenital, oro-pharyngeal-laryngeal (OPL), facial, and peripheral locations. The patient or parent/legal guardian will complete the form by placing vertical marks on each of the 100 mm horizontal lines provided to answer each short question related to the severity of symptoms and the patient's condition. Special attention should be given to patient and parent/legal guardian instructions on the use of the VAS prior to an attack (e.g. at screening and at the baseline assessment of each treated attack). Investigators should make sure that the various scales and the low and high end extremes are well understood, by discussing them extensively with patients and their parents/legal guardian.

Safety of Ruconest in 2-13 year old HAE patients

Each of the VAS instruments provides a patient assessment of the intensity of a range of symptoms pertinent to a symptomatic anatomical location. The Abdominal VAS instrument measures the patient's perceptions relating to four symptoms (illness, pain, bloatedness, and nausea), the OPL VAS instrument measures six symptoms (illness, pain, swelling, breathing, speech, and swallowing), the facial VAS instrument measure three symptoms (illness, pain and swelling), the Peripheral VAS instrument measures three symptoms (swelling, pain, and use of extremity), and the Urogenital VAS instrument measures five symptoms (illness, pain, swelling, nausea, and urination). Additionally, the last question for each attack location is an overall severity VAS for a global assessment of the intensity of the symptoms at that particular location. The wording of the overall severity VAS question is the same for each of the four anatomical location VAS instruments. Examples of the forms are attached as [Appendix B](#).

In addition to completing the VAS forms, patients will answer 3 questions related to the change in severity of their symptoms since the initial assessment. This Treatment Effect Questionnaire (TEQ) will be administered (following confirmation of eligibility) with the VAS for each symptomatic anatomical location. An example of the questionnaire is attached as [Appendix C](#)). If needed, depending on the patient's level of understanding, parents may assist in completion.

In case of a new attack location, additional forms (VAS and TEQ) will be provided for the patient/legal guardian to complete and the time will be recorded.

The patient should be observed for 4 hours in the hospital. After each assessment before discharge of the patient from clinical observation, the forms will be stored in the patient's file and will not be available for review by the patient or parent/legal guardian or investigator to preserve non-biased assessment at each time point by both the patient and study physician. The exception to this will be the moment at which the investigator judges the patient's condition well enough for discharge from the hospital, enabling the investigator to verify the patient/parent scores.

The assessment of the angioedema signs by the VAS and TEQ will be performed just before start of infusion, and at T30m, T1h, T2h, T4h, T8h and T24h after study medication infusion as shown in [Appendix A](#).

In a diary, dispensed at discharge from the hospital, the patient will be asked to record the moment at which all angioedema symptoms at all locations have resolved (complete resolution). If needed, depending on the patient's level of understanding, parents may assist in completion.

The investigator will assess the severity of the patient's angioedema symptoms using an IS for each affected anatomical location (see example in [Appendix D](#)). In case of a new attack location, additional IS-scores will be recorded. The investigator symptoms score will be assessed at presentation of the acute angioedema attack and at 30m, 1h, 2h, and 4h after study medication infusion as shown in [Appendix A](#). All results of assessments will be documented in the CRF.

10.2.4 Study visit procedures

The sections below list the procedures to be performed for each of the planned time points, as shown in the Schedule of Assessment (see [Appendix A](#)).

